1.0 Objectives

The primary objective of this protocol is to evaluate the ability of armodafinil to reduce patient-reported fatigue in patients with treated head and neck cancer.

The secondary objective of this protocol is to explore the effect of armodafinil in reducing symptom severity, symptom interference, patient-reported alertness, work productivity and activity impairment.

2.0 Rationale

Fatigue is one of the most severe symptoms reported by patients at any time point assessed in our M. D. Anderson Symptom Inventory - Head and Neck Module studies (Rosenthal et al, ASCO 2010, Rosenthal et al, ASTRO 2010). Further, fatigue severity peaks for approximately one-fourth of patients after treatment completion, and approximately one-third of patients report moderate to severe fatigue at 8 weeks after completion of radiation therapy or chemoradiation (Rosenthal, ASTRO 2010). This is an important time for fatigue-symptom intervention, because many patients are expecting to return to work or to their usual level of functioning around this time frame.

The agent to be tested in this trial is **armodafinil**. Using a blinded, randomized placebo-controlled trial, we will evaluate armodafinil's ability to reduce patient-reported fatigue in patients with persistent moderate to severe levels of fatigue after completion of radiation therapy and all planned cancer therapy. The target of action for the proposed intervention is armodafinil's alertness-promoting property, which could impact patient-reported fatigue, other associated symptoms, and symptom interference with daily activities.

The significance of this research is that it (1) evaluates a commercially available, low-toxicity symptom therapy, (2) evaluates a therapy that could reduce multiple commonly reported symptoms in patients with head and neck cancer by targeting fatigue (one of the most severe symptoms reported by this patient group), and (3) seeks to establish a simple medical symptom-intervention therapy for head and neck cancer, a disease site for which the patient-reported symptom burden is high and few proven medical symptom intervention strategies exist.

3.0 Background

Cancer was diagnosed in more than 1.4 million people in the United States in 2007 alone — 34,360 with head and neck cancer (HNC) (Jemal et al., 2007). Many of these patients receive aggressive therapy and experience multiple symptoms that cause them significant distress and impair function and rehabilitation. Whereas symptoms are often the result of disease, it is increasingly recognized that pain, fatigue, sleep disturbance, cognitive dysfunction, and affective symptoms can also be caused by cancer treatment. Treatment-related symptoms can directly affect survival if they become so severe that the patient abandons potentially curative therapies (Borden & Parkinson, 1998; Jeremic et al., 2003). Moreover, treatment-related symptoms may persist for weeks, months, or years and may worsen, even if the cancer improves.

3.1 Symptom Management

Better symptom management, in cancer as well as in other diseases, has *been hampered by the lack of a strong clinical-trial evidence base for guiding symptom-management practice*. Several barriers have hindered the development of clinical trials in symptom management. First, the subjective nature of symptoms has limited innovative research into the mechanisms underlying these symptoms and the development of novel ways of treating or preventing them. Special difficulties include the poor fit of current disease models of research for implementing this kind of health-related investigation and lack of statistical models that integrate "rough" self-report data and biologic data (Cleeland, 2001). However, patient-reported outcomes research has recently been promoted by the U.S. Food and Drug Administration (FDA) for more accurate therapeutic agent evaluation, and symptom reduction has been recognized as a primary clinical benefit for drug approval (FDA, 2009).

One approach to symptom-directed treatment could include the more routine use of currently available agents such as stimulants (e.g., **armodafinil**) to modify symptom expression at the central nervous system level.

3.2 Head and Neck Cancer Treatment Side-Effects

All cancer therapies, especially multimodality and multiagent treatment programs, are associated with a spectrum of early and late adverse effects. Although chemoradiotherapy for HNC has consistently been shown to yield clinically relevant improvement in locoregional control and overall survival, these benefits are offset by severe early toxicities (Pignon et al., 2000). One recent analysis noted an almost 500% increase in the number of early toxicity events with chemoradiation as compared with standard radiotherapy for HNC (Trotti et al., 2007). Even so, many patients treated with radiation therapy alone report high symptom burden and functional interference, even after treatment completion. For this reason, and because there is a wide variety of symptoms, ranging in severity, and since they can be transient in nature, physician-reported toxicity data is difficult to evaluate. Thus patient-reported symptom burden may be a better candidate for clinical investigation.

4.0 Background Drug Information

Armodafinil (Nuvigil®, manufactured by Cephalon, Inc) is the R-isomer of racemic modafinil (R-modafinil).

It is indicated for narcolepsy, obstructive sleep apnea, and shift-work sleep disorder, and for improving wakefulness in patients with excessive sleepiness, similar to modafinil.

The usual dosing is 150mg to 250mg per day, given once in the morning or one hour prior to shift work (Prod Info NUVIGIL™ oral tablets, 2008).

Armodafinil's exact mechanism for wakefulness producing is unknown. In vitro, both armodafinil and modafinil bind to the dopamine transporter and inhibit dopamine reuptake, but have no dopamine receptor agonist activity. The wakefulness-promoting actions of armodafinil are similar to that of sympathomimetic amines, such as amphetamine and methylphenidate, despite differences in their pharmacologic profiles (Prod Info NUVIGIL™ oral tablets, 2008).

Modafinil has been shown in clinical studies to have a beneficial effect on fatigue in patients with depression (Thase et al., 2006), narcolepsy (Becker et al., 2004), fibromyalgia (Pachas, 2003), multiple sclerosis (Zifko et al., 2002), and HIV (Rabkin et al., 2004). Studies have reported effect sizes (ES) ranging from 0.57 (Zifko et al., 2002) on fatigue in multiple sclerosis to 0.79 in patients with narcolepsy (Becker et al., 2004).

Pharmacokinetic studies have indicated that even though modafinil and armodafinil have similar half-lives, armodafinil exhibits higher plasma concentration late in the day compared with modafinil on a milligram-to-milligram basis. This difference is due to the stereospecific differences in elimination of the two isomers, which may result in fundamentally different durations of action and may potentially increase the activity of armodafinil throughout the dosing period compared with modafinil. These differences between the two medications cannot be made equivalent by increasing the dose of the racemate, modafinil, without introducing potential safety concerns. Therefore, we have decided to use armodafinil as the active agent for our study.

The safety and effectiveness of NUVIGIL in individuals older than 65 years have not been systematically evaluated. One open-label study showed decreased clearance and an increased half-life in volunteers over the age of 65 years. A lower dose of NUVIGIL should be considered in elderly patients because elimination of NUVIGIL and its metabolites may be reduced as a consequence of aging (Darwish et al, 2010).

To our knowledge, there are no published cancer-related studies with armodafinil. Studies of modafinil, however, have shown its beneficial action on cancer symptoms. A randomized, placebo-controlled, double-blind phase III trial showed modafinil was effective in improving fatigue in cancer patients receiving chemotherapy, although only for patients with severe baseline fatigue scores (Jean-Pierre et al, 2010). A pilot study of 30 patients with brain tumors receiving therapy showed reductions in fatigue severity scores at 8 weeks (ES 1.14) and at 12 weeks (ES 1.21) (Kaleita et al., 2006). In studies of noncancer diseases, the effect size of modafinil in reducing fatigue has been reported to be between 0.57 (multiple sclerosis, Zifko et al., 2002) and 2.00 (biliary cirrhosis, Jones & Newton, 2007). Studies have reported its beneficial effect on mood and cognition (MacDonald et al., 2002; Taneja et al., 2007). Compared with placebo, modafinil improved cognitive performance in breast cancer survivors who had shown a favorable response to modafinil in the preceding open-label phase of the same study (Kohli et al., 2007). Modafinil has been used to augment treatment with selective serotonin reuptake inhibitors (SSRIs) or bupropion in patients with major depression accompanied by residual fatigue and sleepiness (DeBattista et al., 2003; Konuk et al., 2006). Modafinil has also been used to combat opioid-induced sedation in patients with chronic pain (Webster et al., 2003).

Armodafinil is commercially available as 50mg, 150mg, and 250mg tablets. We will purchase commercial grade drug and matching placebo to be dispensed by the investigational pharmacy.

4.1 Absolute Contraindications, Cautions, and Warnings about Armodafinil

4.11 Absolute Contraindications

4.111 Pre-existing psychosis or bipolar disorder

4.112 Pre-existing renal impairment; Severe chronic renal failure (CrCl < or = 20 mL/min) increased modafinil acid 9 fold

4.113 Pre-existing cirrhosis or hepatic impairment

4.114 Pre-existing Tourette's syndrome

4.115 Patient should not be breastfeeding, pregnant, or planning to become pregnant while on armodafinil

4.12 Cautions and Warnings

4.121 Avoid in patients with a history of clinically significant cutaneous drug reaction, or a history of clinically significant hypersensitivity reaction, including multiple allergies or drug reactions

4.122 Caution in patients with a history of angina or cardiac ischemia, a recent history of myocardial infarction or left ventricular hypertrophy, or in patients with mitral valve prolapse

4.123 Induces CYP3A, so avoid midazolam and drugs that are substrates for CYP3A4/5, such as cyclosporine, ethinyl estradiol, triazolam, as dose modification would be needed

4.124 Avoid CYP3A4/5 inducers: carbamazepine, Phenobarbital, rifampin; or inhibitors: ketoconazole, erythromycin

4.125 Moderately inhibits CYP2C19, so avoid omeprazole and drugs that are substrates for CYP2C19, such as phenytoin, diazepam, propantheline, chlomipramine and other tricyclic antidepressants

4.126 Avoid other use in combination with other CNS stimulants, such as methylphenidate, dextroamphetamine, and modafinil

4.127 Caution in combination with MAO inhibitors

4.128 Increased monitoring needed for patients on Coumadin/warfarin

4.129 Clearance may be reduced in the elderly; safety not established for patients over 65

- 4.130 Avoid in patients with history of CNS stimulant abuse, such as methylphenidate, dextroamphetamine, and modafinil
- 4.131 Patients should be cautioned about operating an automobile or other hazardous machinery until they are reasonably certain that armodafinil will not affect their ability to engage in such activities
- 4.132 Steroidal contraceptive effectiveness may be reduced while on armodafinil and for the following month after discontinuing armodafinil – alternative birth control methods recommended during this period

- 4.133 Patients should be advised to avoid alcohol

4.2 Armodafinil Common Adverse Reactions

Most commonly reported adverse reactions: headache, nausea, dizziness, and insomnia

- 4.21 Occurring in greater than >10% of study subjects across randomized studies with armodafinil:

Central nervous system: Headache (14% to 23%)

- 4.22 Occurring in 1% to 10% of study subjects across randomized studies with armodafinil:

Cardiovascular: Palpitation (2%), increased heart rate (1%)

Central nervous system: Dizziness (5%), insomnia (4% to 6%; dose related), anxiety (4%), depression (1% to 3%; dose related), fatigue (2%), agitation (1%), attention disturbance (1%), depressed mood (1%), migraine (1%), nervousness (1%), pain (1%), pyrexia (1%), tremor (1%)

Dermatologic: Rash (1% to 4%; dose related), contact dermatitis (1%), hyperhidrosis (1%)

Gastrointestinal: Nausea (6% to 9%; dose related), xerostomia (2% to 7%; dose related), diarrhea (4%), abdominal pain (2%), dyspepsia (2%), anorexia (1%), appetite decreased (1%), constipation (1%), loose stools (1%), vomiting (1%)

Genitourinary: Polyuria (1%)

Hepatic: GGT increased (1%)

Neuromuscular & skeletal: Paresthesia (1%)

Respiratory: Dyspnea (1%)

Miscellaneous: Flu-like syndrome (1%), thirst (1%)

- 4.23 Postmarketing and/or case reports: Anaphylactoid reaction, angioedema, hypersensitivity, liver enzymes increased, pancytopenia, systolic blood pressure increased (see section on Serious adverse events for symptom drug below)

4.3 Armodafinil Monitoring Parameters

Monitoring Parameters: Signs of hypersensitivity, rash, psychiatric symptoms, levels of sleepiness, increased blood pressure and pulse rate, and drug abuse

- 4.31 Evidence:

Rash: Rash occurred in 2% (n=645) of patients receiving armodafinil (250 mg and 150 mg) compared with 0% of patients receiving placebo (n=445) in clinical trials. Approximately 0.8% of pediatric patients discontinued treatment due to rash, which occurred within a median of 13 days of therapy. Rash appeared to be dose-related in patients taking armodafinil for narcolepsy and shift work sleep disorder. Rash occurred in 4% (n=198) of patients receiving armodafinil 250 mg and in 1% (n=447) of patients receiving armodafinil 150 mg compared with less than 1% of patients receiving placebo in controlled clinical trials (Prod Info NUVIGIL(TM) oral tablets, 2008).

Blood pressure and heart rate: Monitoring of blood pressure may be appropriate, as small but consistent changes in systolic and diastolic blood pressure readings have been seen, ranging from 1.2 to 4.3 mmHg increase. (Prod Info NUVIGIL(TM) oral tablets, 2008). Small but consistent changes in pulse rate have been seen, ranging from 0.9 to 3.5 bpm increase. Prod Info NUVIGIL(TM) oral tablets, 2008).

4.4 Armodafinil (or Modafinil) Drug Interactions

Induces CYP3A, so avoid midazolam and drugs that are substrates for CYP3A4/5, such as cyclosporine, ethinyl estradiol, and triazolam, as dose modification would be needed

Avoid CYP3A4/5 inducers: carbamazepine, Phenobarbital, rifampin, aminoglutethimide, naftilin, nevirapine, phenytoin; or inhibitors: azole antifungals, clarithromycin, diclofenac, doxycycline, erythromycin, imatinib, isoniazid, nefazodone, nicardipine, propofol, protease inhibitors, quinidine, telithromycin, and verapamil

Moderately inhibits CYP2C19, so avoid omeprazole and drugs that are substrates for CYP2C19, such as phenytoin, diazepam, propanolol, chlomipramine (or other tricyclic antidepressants), citalopram, methsuximide, and sertraline

Oral contraceptives: Serum concentrations may be reduced (due to metabolism enzyme induction); contraceptive failure may result; alternative contraceptive measures are recommended during therapy and for 1 month after armodafinil is discontinued

Warfarin: Serum concentrations/effect may be increased by modafinil; would require increased PT/INR monitoring

4.6 Storage Information

Store at 20°C to 25°C (68°F to 77°F)

4.70 Serious Adverse Events for Symptom Drug

Serious and life-threatening rashes have been reported with modafinil and include: Stevens-Johnson Syndrome, toxic epidermal necrolysis, and drug rash with eosinophilia and systemic symptoms. In clinical trials of modafinil, these rashes were more likely to occur in children; however, in the postmarketing period, serious reactions have occurred in both adults and children. Most cases have been reported within the first 5 weeks of initiating therapy; however, rare cases have occurred after prolonged therapy. No risk factors have been identified to predict occurrence or severity of these reactions (Lexi-Comp online, Lexi-Comp, Inc. 1978-2010).

Patients will be advised to discontinue drug at first sign of body rash during this study.

Supplemental NDA 20-717 2 Cephalon, Inc., Provigil® (modafinil) Tablets (C-IV) Version 1.6;

http://www.fda.gov/ohrms/dockets/ac/03/briefing/3979B2_01_Cephalon-Provigil.pdf

[http://www.fda.gov/ohrms/dockets/ac/07/slides/2007-4325s2_10_Modafinil%20Flowers,%20RPh%20\(FDA\).pdf](http://www.fda.gov/ohrms/dockets/ac/07/slides/2007-4325s2_10_Modafinil%20Flowers,%20RPh%20(FDA).pdf)

[figure not shown]
5.0 Study Design

Using a Phase II blinded, randomized placebo-controlled trial, with optional open label extension period, we will evaluate armodafinil's ability to reduce patient-reported fatigue in patients with treated head and neck cancer. This type of trial design is especially important in trials where symptom reduction is the outcome and where knowledge of the treatment arm might bias assessment by the staff or patient. We will purchase commercial grade drug and matching placebo to be dispensed by the investigational pharmacy.

Design: Phase II blinded, randomized placebo-controlled trial, with optional open label extension period

Symptom Intervention Agent: Armodafinil

Study Period: 8-12 weeks depending on participation in the optional open label component : intervention agent daily for 4 weeks (Part I), with continued assessment follow-up period of 4 weeks (Part II). At the end of the 4-week agent intervention, the patient will be given the option to receive open label armodafinil during the 4 weeks follow-up period. If the patient agrees to this option, the follow-up period for these patients will be extended for another 4 weeks.

Primary Symptom Outcome Variable: 4-week (+/- 7 days) area under the curve (AUC) for patient-reported fatigue at its worst (item from the Brief Fatigue Inventory).

Secondary outcomes assessed will include: (1) the 5 most-severe MDASI-HN symptoms at 2-month follow up based on previously collected MDASI-HN data (2) overall MDASI-HN symptom severity, (3) overall MDASI-HN interference, (4) patient-reported alertness (via Epworth Sleepiness Scale), and (5) work productivity and activity impairment questionnaire.

Forty patients will be randomized to either armodafinil or placebo, twenty in each arm. AUC values for patients who drop out of the study after providing 2 weeks of AUC data will be included by carrying their last symptom data forward for the remaining study period under the intent-to-treat rule. The carry-forward method of handling drop-outs will be revisited upon completion of the study to determine if adjustments to these values can be made using longitudinal regression models estimated from patients who completed the entire study.

A list of adverse events (AEs) known to be associated with primary treatment is listed in section 4.0 of the protocol. Study staff will monitor for AEs via telephone contact with the subjects using the Phone Contact Form according to the Assessment Schedule. In addition, study participants will be able to contact study personnel via a telephone hotline, and study participants can be seen by study personnel at MD Anderson if there are any concerns or questions regarding potential side effects. If seen in person by study personnel, clinical monitoring form will be completed. Also, if study subjects are coming to MD Anderson for

routine clinical follow up (visits unrelated to this study), they will be seen by study staff as frequently as weekly during the study period, and the clinical monitoring form will be completed every time.

Patients will be advised to discontinue drug at first sign of body rash during this study and to immediately notify study personnel, who will in turn notify the PI for appropriate medical management.

All grade 3 and 4 toxicities reported by patients in this trial will be evaluated by the principal investigator in consultation with the treating physician, or by another attending physician if the PI is not available, to determine whether the toxicities were possibly caused by the study medication (rather than being effects from previous cancer therapy). The investigators will discriminate between expected dermatitis related to radiation therapy or chemotherapy versus armodafinil hypersensitivity. If 1 or more armodafinil-related grade 3 or 4 toxicities is observed in the patients assigned to armodafinil, the study will be terminated.

The interaction screening will be the responsibility of the research staff. Study exclusion criteria of known drug interactions and drugs that would require additional monitoring if given in conjunction with armodafinil will also be in place for patient safety. The research staff will review any current or new patient medications prior to initiating treatment, and will document all medications patients have used or will use during the trial. During the trial, the research staff will capture any potential drug interactions that could cause an AE on the Adverse Event forms. Medication sheets will be provided to both patients and treating physicians to inform them of the possibility that the patients may be receiving armodafinil (see Appendix EEE and EE).

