6.0 Administration of Pharmacologic Agent

Armodafinil or placebo will begin after enrollment and will continue daily for a total of 4 weeks.

Patients will pick up the assigned study medication at one of the outpatient pharmacy stations in MD Anderson. At pickup, patients will receive instruction on how to take study medications (Appendix EEE). If the patient is unable to pick up the study medication, the investigational pharmacy will mail the study medication to the patient home, overnight.

The participants will take study medication enterally, once daily, in the morning, starting after study entry and continuing for 28 days (4 weeks). The dosing schedule for the symptom intervention agent is described in the table below.

Study medication use will be reviewed at the end of week 4 by study staff. Patients will be asked to bring their study medication to the clinic if they are coming in for a routine visit, at which time study staff will perform a medication count. If the patient is not coming to the clinic at study completion, the medication review will be completed by telephone. Results of the count will be recorded on the Study Medication Accountability form (Appendix K).

During the end of week 4 assessment, the study staff will also offer the participant the option to receive open label armodafinil, at the same dosing schedule described in the table below. If the patient agrees to the optional open label extension, they will either pick-up armodafinil during their routinely scheduled follow-up visit or the pharmacy will mail it to them. A 5-day window will be allowed between the end of Part I and the start of the optional open label extension.

Symptom Intervention Agent	Dosage Forms	Total daily dose: starting day 1 of week 1
Armodafinil or matching placebo	50mg and 100mg capsules or tablets	50 mg the first 3 days, 100 mg the next 4 days, and 150 mg for the remaining treatment period.*

*capsules or tablets, one every morning, may be given without regard to meals. This dosing schedule is to be followed during the 4-week symptom intervention and the optional open label extension.

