13.0 Statistical Analysis Plan

13.1 Sample Size and Randomization

Forty patients will be randomized equally to the 2 treatment arms - armodafinil and placebo. With 20 patients per treatment arm, we will be able to detect a 0.70 SD effect size on the BFI AUC between the 2 treatments with 70% power and one-sided 5% significance test. A 0.70 effect size for the BFI is about **1.7 points (change in terms of AUC)** on a 0 to 10 scale. Because this is a small Phase II study with the intent of providing effect size estimates to inform a large clinical trial in the future, we chose a modest statistical power.

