13.2 Analysis Plan

We will test armodafinil in its ability to reduce values of patient- reported fatigue scores. Our emphasis is to test the efficacy of armodafinil as a potential agent in reducing patient-reported symptoms in patients with HNC after planned cancer therapy. The proposed phase II clinical trial for screening this potentially effective symptom-intervention agent will provide moderate power in detecting modest intervention effect. If the treatment has a more pronounced effect, it will be detected with higher power.

This study will allow us to obtain estimates of treatment effect and the variability of these estimates. Estimates of treatment effect will be obtained using standard linear regression techniques in which AUC values ($hn(i)$) are regressed on indicator variables that represent treatment received. Estimates of treatment effect and between-subject variability will then be used to design a more comprehensive study in future clinical trials.

In addition to the formal evaluation of treatment effects on the primary outcome, we will also examine the prognostic effects of disease stage, type of cancer treatment, ECOG status, age and gender in predicting the outcome variable. We will compare the percentages of patients who were satisfied with the study drug against those who were taking the placebo. We will include an indicator variable in our model to determine whether patients who had a full dose of armodafinil differ from those who had a run-in period. Standard exploratory data analysis techniques and descriptive statistics will be used.

Assuming that patients accrue at the rate of 4 per month, we anticipate that this pilot study will require approximately 14 months to complete.

Intent to treat

We will need at least 2 weeks of BFI data for the patient to calculate AUC. Any patient who drops out prior to this will be replaced.

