13.21 Primary Outcome Variable

The primary outcome variable will be the combined AUC for the “fatigue at its worst” item of the BFI. The value of this variable for patient i is denoted $bfi(i)$ and is comprised of the BFI scores collected during the 8 weeks of the study period.

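### The primary 4-week (+/- 7 days) fatigue AUC has no stated divisor or common end day, so if computed as a raw area it would vary with the date of the last rating as well as with fatigue.

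*Combined protocol and SAP*

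**What the plan says.** Section 5.0 gives the primary outcome as the "4-week (+/- 7 days) area under the curve (AUC) for patient-reported fatigue at its worst". Patients who drop out after at least 2 weeks of data are included by "carrying their last symptom data forward for the remaining study period under the intent-to-treat rule". No rule is given for a patient who stays in the study but is rated early or late.

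Section 13.21 names the outcome bfi(i): "The primary outcome variable will be the combined AUC for the “fatigue at its worst” item of the BFI". It adds that this "is comprised of the BFI scores collected during the 8 weeks of the study period", which conflicts with the 4 weeks of section 5.0. Section 13.2 writes the AUC as hn(i), and these values "are regressed on indicator variables that represent treatment received". No section gives an integration rule, a unit, a divisor or a common end day.

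The only indication of scale is in section 13.1: "A 0.70 effect size for the BFI is about" 1.7 points, described as a change in AUC on a 0 to 10 scale.

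Section 6.0 sets blinded dosing at 28 days and has staff offer open-label drug at the week-4 assessment. "A 5-day window will be allowed between the end of Part I and the start of the optional open label extension".

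**The concern.** A raw area under a curve grows with the time it covers. On its natural reading, 4 weeks plus or minus 7 days lets one patient's curve end on day 21 and another's on day 35. With no divisor and no common end day, two patients with identical fatigue could then have different primary outcomes.

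Timing unrelated to treatment would add noise to a trial already planned at 70% power. Timing that differed by arm would shift the estimated treatment effect. The trial is meant to supply effect-size and variability estimates for a larger study, and both would carry the timing component.

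There is also a question of content. A rating on days 29 to 35 describes fatigue after the blinded course has ended, and possibly after open-label drug has begun.

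The point does not depend on how the 4-week and 8-week spans are reconciled. It remains if 4 weeks is confirmed.

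**Working it through.** **Inputs from the documents.** 20 patients per arm, effect size 0.70 SD, one-sided 5%, power 70%, effect about 1.7 points on 0 to 10 (section 13.1); window of 4 weeks +/- 7 days (section 5.0); 28 days of blinded dosing (section 6.0); worst fatigue of 4 or less excluded (section 8.21).

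**Assumptions, not in the documents.** The spread of last-rating days; a mean level of 5 to 7 over the period; timing independent of fatigue and of arm, except in step 5.

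**1. The plan's own figure.** Noncentral t with 38 df: noncentrality 0.70 × √(20/2) = 2.21, critical value 1.686, power 70.2%. The stated 70% is reproduced.

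**2. Unit.** Implied SD = 1.7 / 0.70 = 2.43 points. As a raw 28-day area, the SD would be 2.43 × 28 = 68 and the effect 1.7 × 28 = 47.6 point-days, on a range of 0 to 280. So 1.7 cannot be in raw point-days; it fits an average over time.

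**3. A constant rating, as a raw area (level × days).**

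| Level | Day 21 | Day 28 | Day 35 | 7-day shift on the 28-day-average scale |
|---|---|---|---|---|
| 5 | 105 | 140 | 175 | 5 × 7/28 = 1.25 |
| 6 | 126 | 168 | 210 | 6 × 7/28 = 1.50 |
| 7 | 147 | 196 | 245 | 7 × 7/28 = 1.75 |

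The swing is 25% either way. It is the extreme for one patient and should not be read as a difference between arm means. Divided by days, each row gives its own level at every end day.

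**4. Power if timing is independent of arm.** With last day T (mean 28) and level μ, the variance of the raw area on the 28-day-average scale is [μ² Var(T) + SD² (28² + Var(T))] / 28².

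At μ = 6, with T uniform on 21 to 35:
- Var(T) = 14²/12 = 16.33.
- Variance = [36 × 16.33 + 5.898 × (784 + 16.33)] / 784 = 6.77, so SD = 2.60.
- Effect size = 1.7 / 2.60 = 0.65, and power is 65%.

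| Last-rating day | Power, μ = 5 | μ = 6 | μ = 7 |
|---|---|---|---|
| SD 2 days | 69% | 69% | 68% |
| Uniform, days 21 to 35 | 66% | 65% | 63% |
| Half at day 21, half at day 35 | 60% | 57% | 53% |

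**5. Only if timing differs by arm.** Bias = μ × shift / 28. A mean shift of 2 days gives 0.36, 0.43 or 0.50 points at μ = 5, 6 or 7, which is 21% to 29% of 1.7. With no drug effect, μ = 6, SD 2.43 and last days spread uniformly within 3 days of each arm's mean, simulation gives a one-sided error of about 8%, 13% or 19% when placebo patients are rated 1, 2 or 3 days later on average. With no shift it stays at about 5%.

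**The case against.** The strongest reply is that the plan never says the AUC is undivided. The one line on scale, in section 13.1, points to a time average, and the +/- 7 days may be only a visit window around a nominal week-4 rating, with the area computed on nominal weeks. In either case rating dates would have little or no effect on the score. This stands as far as intent goes: a reader may not conclude that a raw area was chosen. It does not settle the calculation, because the sections that define and model the outcome state neither rule. The assessment schedule (Appendix X) is not in the text available, so it could not be checked.

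A reader might also take carry-forward as a sign of a raw area, on the ground that an average needs no filling. That does not follow. Ratings of 8, 6 and 4 on days 0, 7 and 14 have an area of 84 and average 84/14 = 6.0; carried to day 28 the area is 84 + 4 × 14 = 140 and the average 140/28 = 5.0. Filling changes an average too, so the rule is silent on division.

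On size, automated calls on set dates (section 7.1) may keep the spread small, and with an SD of 2 days the loss is 1 to 2 percentage points. The inflated error rates require timing to differ by arm in a blinded trial, and nothing in the documents suggests that it would.

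On open-label drug, the offer comes at the week-4 assessment, so a late assessment may also delay the offer. Contamination is possible but not established. What is certain is that days 29 to 35 lie outside the 28-day course.

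The use of hn(i) in one place and bfi(i) in another is a notation slip, since section 13.2 does label hn(i) as the AUC.

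**Conclusion.** The concern holds in a limited form. The primary outcome has a 14-day range of permissible end days and no stated rule that removes the effect of that range. Its definition also does not state the unit on which the sample size rests. Two analysts could follow the plan and obtain different outcomes from the same data.

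If a raw area were used, the likely cost is moderate: power of about 65% under uniform timing and about 69% with a 2-day SD, at a mean level of 6, against 70% planned. The case with everyone at the two ends of the window (53% to 60%) is an outer bound. Timing unrelated to arm would cost power only. The bias and error-rate figures are conditional on arm-related timing and are not a forecast.

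It would go too far to say that the AUC is not divided by days, that completers are definitely followed to their actual last rating, or that open-label ratings definitely enter the primary outcome. The change should be made because it is cheap and fixes the primary outcome before analysis.

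**What to change.** In sections 5.0, 13.2 and 13.21, define bfi(i) as the trapezoidal AUC of BFI worst fatigue from baseline to day 28, using actual rating dates and divided by the days spanned. This is a 0 to 10 score in the unit of section 13.1. Then state:

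- **Late last rating:** interpolate to day 28, or truncate at the last rating on or before it, naming one of the two in advance. Use no rating taken after an open-label dose.
- **Early last rating in a patient who completes:** divide by the actual days.
- **Dropouts with at least 2 weeks of data:** keep the plan's carry-forward to day 28 and divide by 28, so that the divisor does not undo that rule.
- **Notation and span:** replace hn(i) with bfi(i) in section 13.2, and reconcile the 8 weeks of section 13.21 with the 4 weeks of section 5.0.

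The cost is a few sentences and a short change to the analysis code, with no added patients or visits. It needs a date for each rating. The available text does not confirm that dates are kept for every mode of collection, mailed forms included, so this should be checked against Appendix X and the data forms.
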